 - 7.4 Retention and destruction of project data and biological material
- 8. Funding / Publication / declaration of Interests
- REFERENCES
- 9. If applicable: Appendix 1: Schedule of assessments

GLOSSARY OF ABBREVIATIONS

- BASEC Business Administration System for Ethical Committees
- CRF Case report form
- FOPH Federal Office of Public Health
- HRA Human Research Act
- HRO Ordinance on Human

1. BACKGROUND and project rationale

Skin aging is a complex process that involves both intrinsic and extrinsic factors. Intrinsic factors, such as genetic and hormonal changes, play a role in skin aging, while extrinsic factors, such as exposure to UV radiation and environmental toxins, accelerate the aging process. The signs of skin aging include wrinkles, age spots, reduced elasticity, reduced hydration, and increased transepidermal water loss ⁴⁵.

As we age, the body's natural ability to replenish collagen decreases by approximately 1.0%-1.5% per year. This decline in collagen production is a significant factor contributing to the development of fine lines and deeper wrinkles. Additionally, within the deeper layers of the skin (dermis), essential components of the extracellular matrix such as fibrillar collagens, elastin fibers, and hyaluronic acid undergo noticeable structural and functional changes ⁵⁴. The aging process brings about various changes in the different layers of the skin. In the outermost layer, the epidermis, the thin basal lamina that separates it from the dermis becomes thinner, resulting in reduced cell turnover and a thinner epidermis. This leads to decreased barrier function, slower recovery, increased water loss, reduced hydration, and increased stiffness ⁷.

The connection between the epidermis and the dermis, known as the dermal-epidermal junction, weakens with age, contributing to wrinkle formation and further thinning of the epidermis. In the dermis, the second layer of the skin, significant changes occur. Collagen, the predominant protein, undergoes increased fragmentation, leading to fewer fibroblasts and reduced production of type I collagen. Additionally, collagen degradation by matrix metalloproteinases (MMPs) increases, resulting in dermal thinning and the formation of wrinkles ⁷.

Aging also affects elastin, another crucial protein in the skin. Exposure to UV radiation enhances elastin degradation, while reduced synthesis by fibroblasts leads to decreased skin elasticity. Hyaluronic acid, which plays a vital role in skin hydration, experiences a reduction in synthesis, leading to decreased skin hydration⁷.

In conclusion, skin aging is a complex process involving changes in the epidermis, dermal-epidermal junction, and dermis. The signs of skin aging, including wrinkles, age spots, reduced elasticity, reduced hydration, and increased transepidermal water loss, are the result of these changes. Understanding the molecular and cellular mechanisms underlying skin aging can help in the development of effective anti-ageing strategies 57.

Epigenetic methylation clocks are emerging as a promising biomarker of biological age. DNA methylation is a chemical modification of DNA that regulates gene expression and plays a critical role in development and aging. Methylation patterns change over time, and researchers have developed epigenetic clocks based on DNA methylation patterns to estimate biological age ⁸⁻¹².

Accelerated epigenetic clocks, which are associated with older biological age, have been linked to several health outcomes. Studies have shown that accelerated epigenetic clocks are associated with mortality, cardiovascular disease, cancer, diabetes, and higher BMI ¹³⁻¹⁷. Intervention studies have used epigenetic clocks to show a reduction in biological age. For example, diet and lifestyle interventions have been shown to reduce biological age, as measured by epigenetic clocks ¹³⁻²⁰. Additionally, supplementation with alpha-ketoglutarate has been shown to decrease biological age ²¹. These findings suggest that epigenetic clocks may be useful in evaluating the efficacy of interventions aimed at improving health and longevity. Our trial provides an opportunity to further establish the correlation between epigenetic clocks and relevant health measures. By measuring DNA methylation patterns and biological age in our participants, we can evaluate the relationship between epigenetic clocks and health outcomes, in our case multiple measures of skin aging. These findings may provide insights into the mechanisms underlying aging and identify new targets for interventions aimed at improving health and longevity.

Skin measurements are essential tools for evaluating the efficacy of interventions aimed at improving skin health and appearance. The Corneometer is a commonly used device for measuring skin hydration. Several studies have shown that oral collagen peptide supplements can improve skin hydration, as measured by the Corneometer, over a period of two to three months ^{22–28}. However, one study found no improvement in skin hydration with collagen peptide supplementation ²⁹.

Skin elasticity is another important measure of skin health. The Cutometer is a device commonly used to measure skin elasticity. Studies have shown that oral collagen peptide supplements can improve skin elasticity, as measured by the Cutometer, over a period of two to three months ²²⁻³¹. However, one study found no improvement in skin elasticity with marine collagen supplementation ³².

Skin thickness is also an important measure of skin health. Ultrascan is a non-invasive method for measuring the thickness of the epidermis and dermis, as well as collagen density. Studies have shown that oral collagen peptide supplements can improve skin thickness, as measured by sonography, over a period of two to three months ^{24,30}.

Overall, these skin measurements provide valuable information on the efficacy of interventions aimed at improving skin health and appearance. Oral collagen peptide supplements have been shown to improve skin hydration, elasticity, and thickness in several studies. However, some studies have found no improvement in skin hydration or elasticity with collagen peptide supplementation. These inconsistencies may be due to differences in the type, dose, and duration of collagen peptide supplementation, as well as individual variations in response to supplementation.

In addition to the information provided, Visia skin analysis is another widely used tool for evaluating skin health and appearance. Studies have shown that oral marine collagen and hydrolyzed collagen supplements a can lead to a reduction in wrinkles over a period of two to three months, as measured by Visia skin analysis. The effectiveness of collagen peptide supplements in improving skin health and appearance has also been evaluated using the Miravex Antera 3D system, which provides a comprehensive analysis of skin texture, pigmentation, and vascularization.

Several studies have been conducted to validate the Visia system, including those by Hensler et al. ³³⁻³⁵ and Wang et al. ³⁶. These studies have demonstrated the reliability and accuracy of the Visia system in measuring skin parameters such as wrinkles, pigmentation, and pore size.

Overall, these skin measurement tools provide valuable information on the effectiveness of collagen peptide supplements in improving skin hydration, elasticity, thickness, and reducing wrinkles and other signs of aging. However, it is important to note that individual variations in response to supplementation may exist, and further research is needed to determine the optimal type, dose, and duration of collagen peptide supplementation for improving skin health and appearance.

The justification for categorizing the clinical trial involving a *collagen activator* and non-invasive measurements as risk category A is based on the fact that the intervention is considered low risk and has a well-established safety profile. The *collagen activator* supplement is freely available on the market. Participants are taking the *collagen activator* voluntarily and the potential risks associated with taking the supplement are minimal, with no known serious adverse effects reported.

In addition, the measurements involved in the study are all non-invasive and have been widely used in clinical research. The use of the corneometer, cutometer, ultrascan, and Visia scan are considered standard techniques for measuring skin hydration, elasticity, thickness, density, pigmentation, wrinkles, texture, UV-spots, pores, redness, and porphyrins. These measurements are safe and pose no known risks to participants when used by trained personnel.

Furthermore, the spit test used to measure biological age with an epigenetic methylation clock is also non-invasive and has been used in previous clinical trials. The use of this test

poses no known risks to participants and is a well-established technique for measuring biological age.

Therefore, based on the low-risk nature of the intervention and the non-invasive measurements involved, this clinical trial can be justified as risk category A.

2. project OBJECTIVES and Design

2.1 Hypothesis and primary objective

Primary objective: Intake of the collagen activator from Avea for 6 months will result in a significant decrease in biological age compared to the baseline.

Secondary objective: Intake of the collagen activator from Avea will lead to a significant improvement in skin quality and texture, including increased hydration, elasticity, and reduction in wrinkles, pigmentation, texture, UV-spots, pores, redness, and porphyrins after 3 months compared to baseline.

2.2 Primary and secondary endpoints

The primary endpoint of our trial is to assess changes in DNA methylation patterns as a biomarker of biological age after the intake of the collagen activator from Avea for 6 months. Epigenetic clocks, based on DNA methylation patterns, have been shown to be associated with various health outcomes such as mortality, cardiovascular disease, cancer, diabetes, and higher BMI in several studies including Lau et al., McCrory et al., Föhr et al., Oblack et al., and Lo et al.^{13,16-17,37}.

Therefore, the rationale for using DNA methylation patterns as a biomarker of biological age is to investigate whether the intervention with the collagen activator can slow down the accelerated epigenetic clocks and potentially reduce the risk of age-related health conditions. Previous intervention studies using epigenetic clocks have shown promising results in reducing biological age through dietary and lifestyle interventions, alpha-ketoglutarate, and other lifestyle interventions, as demonstrated by Fitzgerald et al., Demidenko et al., Duan et al., Fiorito et al., and Pavanello et al.

In addition, our trial aims to establish the correlation between epigenetic clocks and relevant skin health measures. To control for potential baseline factors that might influence the outcome, we will consider factors such as gender, age, chronic diseases and smoking. By investigating changes in DNA methylation patterns, our trial will provide valuable insights into the efficacy of the collagen activator in improving cellular and tissue health and potentially reducing the risk of age-related health conditions.

Secondary endpoints:

- Hydration (measured with the corneometer): Baseline factors we consider that can influence hydration levels are age, gender, and skin type. Adequate hydration is important for maintaining skin health and preventing dryness and roughness.
- Elasticity (measured with the cutometer): Baseline factors we consider that can influence skin elasticity are age, sun exposure, and smoking. Good skin elasticity is a sign of healthy, youthful skin.
- Skin thickness and density (measured with the ultrascan): Baseline factors we consider that can lead to thinning of the skin are age and sun exposure. Measuring skin thickness and density can help determine the overall health of the skin.
- Pigmentation, wrinkles, texture, UV-spots, pores, redness, and porphyrins (measured with the Visia scan): Baseline factors we consider that can influence these factors are age, sun exposure, smoking, and genetics. These measurements can help determine the overall appearance and health of the skin.

These measurements contribute to determining skin quality and texture by providing objective and quantitative data on various aspects of the skin. By monitoring changes in

these measurements over time, researchers can assess the effectiveness of the collagen activator aimed at improving skin quality and texture.

2.3 Project design

The study is a human research study in which customers that are taking the collagen activator from Avea are observed for six months. The trial is in the form of a post marketing surveillance observational trial since the product has already been approved and is sold on the market. All participants are voluntarily taking the collagen activator. There is no blinding, randomization or placebo control that is taking place in the trial. The results are compared individually for each participant after the follow ups from their baseline measurements.

- The trial exposure is the Collagen activator from Avea
 - Potential participants are contacted after purchasing the collagen activator for 6 months via Avea's online shop. After successful recruitment they undergo the baseline assessment. They are instructed to only start taking the collagen activator once the baseline assessment is completed.
 - o Daily oral intake of 1 package of 11.5g diluted in water over six months, taken in the morning
- Saliva samples are taken twice (time points 0 and +6 months) to determine biological age via epigenetic methylation clock (Trume labs are the test providers and analysers)
- Skin analysis takes place at time points 0, +1 and +3 months to determine skin quality. This includes measurements of hydration, elasticity, skin thickness and density, as well as pigmentation, wrinkles, texture, UV-spots, pores, redness and porphyrins.
- Skin tests used for this are the corneometer, cutometer, ultrascan and Visia scan.
- Every month the participants receive a questionnaire regarding recent subjective changes, adverse reactions and adherence

The individual duration expected for each patient from the recruitment process onwards is about 6-7 months

- The goal is to recruit 60 healthy participants that are older than 35 years and are voluntarily taking the collagen activator for 6 months
- 2-3 weeks from being recruited to receiving a date for the baseline measurements
- Day 1 being the day of the baseline measurements
- Follow ups for the skin measurements take place +1 and +3 months from day 1
- Follow up for the saliva test takes place +6 months from day 1

The justification for this study design lies in its ability to provide a comprehensive assessment of skin quality and biological age. By measuring a range of skin quality parameters, the study will be able to capture changes in skin texture and appearance over time. Similarly, by measuring biological age using an epigenetic methylation clock analysis, the study will be able to capture changes in biological age over time.

Overall, the use of a combination of skin measurements and biological age measurements provides a robust and comprehensive approach to measuring changes in skin quality and biological age over time with the use of the *collagen activator* by Avea.

To account for the influence of women's menstrual cycle on the skin measurements, the study doctor will ask female participants at each visit about the first day of their most recent menstrual period. This is a standard procedure to determine if a women is in the follicular phase (first 2 weeks from the first day of period) or in the luteal phase (more than 2 weeks from the first day of period). This will be accounted for during the data analysis to reduce confounding. Further, as both females and males are included in this study, sex will be

included as a covariate in the analysis to address potential differences between male and females.

Limitations:

We do not have the means to collect direct data about UV-exposure and try to account for it within the baseline questionnaire. We ask about the usage of sunscreen of participants, specifically how regularly they apply it and which sun protection factor they use, as well as how much time they usually spend in the sun. This will then be considered in the data analysis. Further, it is not possible to do all the skin analyses at a consistent time of day.

3. PROJECT POPULATION and Study procedures

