3.3 Study procedures

The recruitment period will presumably start in August 2023 and the latest follow-up visit for a participant is expected to be in December/January 2023. For an individual participant, the recruitment period will be 1 month or shorter and includes an online screening procedure and phone call with Frau [name] or her team. Participants will be informed about all study details as described in 3.2 via email and time will be given to them to make a decision about the participation and to give informed consent at all times. In case of any questions, they can reach out to the person in charge of recruitment via phone. After successful completion of the screening, a first visit at the Dermatology clinic Hautwerk in Zurich will be scheduled as soon as possible (not later than a month). The participants will receive an online medical questionnaire (via REDcap), which they can fill out at home before the first visit if they are able to, or if not they will fill it out at the first visit under supervision of a medical professional (doctor). At the first visit [name] will go through all the relevant information again with the participants which allows them to give their informed consent and will fill out the informed consent form with them. The participants receive a copy of the signed form.

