- 3. Ultrascan: Ultrascan is a non-invasive device that uses high-frequency ultrasound waves (22 Mhz) to measure the thickness and density of the skin. The device works by emitting ultrasound waves into the skin, which bounce back and are recorded by the device. The time it takes for the ultrasound waves to bounce back is used to calculate the thickness of the skin. This measurement is used to assess the overall health of the skin and collagen content can be read out by it.
- 4. Visia scan: Visia scan is a non-invasive imaging system that captures high-resolution images of the skin's surface. The device uses different types of light, such as UV, polarized, and non-polarized light, to capture images of the skin at different depths. The images are then analyzed to assess various skin conditions, including pigmentation, wrinkles, texture, UV-spots, pores, redness, and porphyrins. This measurement is used to assess the overall health and quality of the skin.

At the time points +1, +2, +3, +4 +5 and +6 months of the study duration, a short online questionnaire will be sent to all participants via email, with a secure link to the REDcap online form. It will contain questions about the product intake (how many days of the months), the health status (any changes, physical or mental illness, adverse reactions), important lifestyle changes, and if the participants are still willing to continue with the study. There will also be the possibility for the participants to reach out to a medical professional or to schedule a visit.

At the timepoints +1 and +3, follow-up visits at the Dermatology clinic Hautwerk will be scheduled (time frame +/- 1 week of the +1 and +3 months time point respectively). The visit will contain the same procedures as the visit at time point 0, minus the saliva sample. The medical professional will again first check the completion of the questionnaire and assist if necessary, then take the skin scan (Visia analysis system), and the tests with the corneometer, cutometer and ultrascan. The participants have then time to rest to make sure there are no adverse reactions to any of the procedures. At time point +3, the participant will be provided with the saliva collection kit for timepoint +6 months. Each visit will be recorded by the medical professional. The total visit should take between 30 to 60 minutes.

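### A baseline-only question on usual sun habits cannot remove the average seasonal change from the uncontrolled pre-post skin comparisons

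*Protocol*

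**What the plan says.** **Which outcomes depend on sun.** Protocol 2.2 lists sun exposure among the factors for elasticity and for skin thickness and density. For the Visia features it says: "Baseline factors we consider that can influence these factors are age, sun exposure, smoking, and genetics". For hydration it lists age, gender and skin type, not sun.

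**What is collected.** The limitations in 2.3 state: "We do not have the means to collect direct data about UV-exposure and try to account for it within the baseline questionnaire". The items are sunscreen regularity, protection factor, "as well as how much time they usually spend in the sun". The promise is: "This will then be considered in the data analysis". The monthly questionnaire in 3.3 is described thus: "It will contain questions about the product intake (how many days of the months), the health status". The list goes on to a general item on lifestyle changes and to willingness to continue. Later in 3.3, illness and large changes in behaviour are given as examples of confounders to be asked about. Neither place names sun.

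**Design.** "Skin analysis takes place at time points 0, +1 and +3 months to determine skin quality" (2.3). "There is no blinding, randomization or placebo control that is taking place in the trial" (2.3). The secondary objective in 2.1 is improvement after 3 months against baseline, and 2.2 treats change over time in these measures as the way to judge effectiveness.

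**Calendar.** "The recruitment period will presumably start in August 2023 and the latest follow-up visit for a participant is expected to be in December/January 2023" (3.3).

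**Model.** Section 4.1 gives the skin endpoints linear regression with sex as a covariate and a paired pre-post structure. It names no term for sun or season.

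**The concern.** If most participants start in late summer or early autumn and are measured again three months later, their sun exposure is likely to fall together over the period in which they take the product. With no concurrent control, a seasonal change in UV-spots, pigmentation or redness looks the same as a product effect. The protocol recognises sun as an influence and says it will account for it, but the variable it collects describes how participants differ from one another, not how their exposure changes between visits.

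Section 2.3 handles a comparable problem differently: menstrual phase varies between visits and is therefore asked at each visit. Sun exposure also varies between visits and is named only at baseline. A later analysis plan cannot repair this, because the data would not exist.

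**Working it through.** **1. Inputs.** Section 4.1 gives one-sided alpha 0.05, power 0.80, effect size 0.5 and n = 50 evaluable. The drift sizes below are assumptions.

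**2. The plan's own figure.** The stated n = 50 is reproduced by the normal two-sample formula per group, n = 2(1.645 + 0.842)²/0.5² = 49.5, rounded up to 50. Drop-out inflation gives 50/0.85 = 58.8, so 59, and 50/0.80 = 62.5, so 63, as stated. With 60 recruited and 15–20% lost, 60 × 0.85 = 51 to 60 × 0.80 = 48 remain, so n = 50 is a fair analysis size for the illustration.

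**3. Calendar of the month-3 skin visit.**

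| Baseline | +3 months |
|---|---|
| 1 Aug 2023 | 1 Nov 2023 |
| 31 Aug 2023 | 30 Nov 2023 |
| 30 Sep 2023 | 30 Dec 2023 |
| 31 Oct 2023 | 31 Jan 2024 |

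Each visit has a window of one week either side.

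**4. What a baseline covariate can do.** Let D be the change from month 0 to month 3, with D = product effect + seasonal drift + error, and let S be usual sun time.

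- In a model for the two visits, a main effect of S is the same at both and cancels in D.
- In a change-score regression D = a + b(S − mean S) + error, the least-squares estimate of a is the raw mean of D. Its expectation is product effect + average drift, whatever b is. In simulation (n = 50, 3,000 runs, assumed drift 0.5 SD, no product effect), the estimate stayed at 0.50 and rejection at about 96%.
- If S is not centred and the effect is read at S = 0, then a = mean D − b × mean S. Suppose a share p of a 0.5 SD drift is proportional to S and the rest is common to all. The expected intercept is then 0.5(1 − p). If S is measured with reliability 0.5, b is halved and the intercept is 0.5(1 − p/2).

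| Share p proportional to sun time | S without error: formula (simulated) | Reliability 0.5: formula (simulated) |
|---|---|---|
| 0 | 0.50 (0.51) | 0.50 (0.49) |
| 0.25 | 0.375 (0.38) | 0.4375 (0.44) |
| 0.50 | 0.25 (0.25) | 0.375 (0.38) |
| 0.75 | 0.125 (0.12) | 0.3125 (0.32) |
| 1 | 0 (0.00) | 0.25 (0.25) |

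The simulation used a gamma distribution for sun time (mean 2, SD 1, assumed). The part of the drift common to all participants is never removed.

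**5. Size, as an illustration.** For a paired t-test with n = 50, one-sided 0.05 and no product effect, the rejection rate is P(T > t(0.95; 49)), where T is noncentral t with 49 degrees of freedom and noncentrality d√50, and d is the favourable drift in SDs of the paired change.

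| d | d√50 | Significant |
|---|---|---|
| 0.1 | 0.71 | 17% |
| 0.2 | 1.41 | 40% |
| 0.3 | 2.12 | 67% |
| 0.5 | 3.54 | 97% |

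The same table shows the opposite risk. A true effect of 0.5 SD offset by an adverse drift of 0.2 SD leaves a net 0.3 SD, so detection falls from 97% to 67%. All rates are per endpoint, before the false-discovery-rate adjustment in 4.1.

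**The case against.** **The weakness is disclosed.** The sentence on UV stands under limitations and promises only an attempt. That stands. What is disclosed, however, is the lack of direct UV measurement. Season is not mentioned.

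**Other items may catch it.** The monthly forms ask about lifestyle changes, and 3.3 promises questions on confounders. The forms are not shown, so these items may pick up a marked change such as a beach holiday. They would not reliably record the ordinary fall in sun from summer to winter, which few people would report as a lifestyle change.

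**The calendar is tentative.** The start is only presumed, and baseline can come up to a month after screening. The stated end date also does not fit an August start plus six months, which is February 2024 at the earliest, if it is meant to cover the second saliva sample. A different start would change the direction or size of the seasonal shift. It would not supply the missing repeat measurement.

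**The root cause is the lack of a control group, which the protocol states openly.** True, and repeated sun questions do not replace one. That limits what the fix can achieve.

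**A stronger reading is tempting:** that the baseline adjustment can remove none of the seasonal change. The documents do not support this. Usual sun habits can explain differences in drift between participants and, read at zero exposure, can remove the part proportional to sun time (step 4). The protocol does not say how the covariate would enter. Only the shared drift is out of reach.

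**Conclusion.** The point holds for the average seasonal change shared by participants. A single habitual sun measure leaves it in the estimated change for elasticity, thickness, density and the Visia features. Hydration is outside the point, because 2.2 does not tie it to sun. The primary saliva endpoint is also outside it.

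The conclusion rests on three things: sun is named only at baseline, there is no concurrent control, and the approximate calendar holds. The percentages are illustrations under assumed favourable drift. A reader might infer that the skin results will be false positives at those rates. The documents give neither the size nor the direction of any drift, so that does not follow.

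Nor should one infer that a change surviving adjustment for current sun exposure would prove effectiveness. If everyone moves towards less sun together, exposure change is nearly collinear with time on product. This is a cheap improvement to secondary endpoints.

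**What to change.** 1. Repeat the existing sunscreen, protection-factor and time-in-sun questions in the month-1 and month-3 questionnaires, referring to the past 4 weeks. Ask them with the same reference period at baseline, so that a change can be calculated. Both questionnaires are already scheduled and checked at the clinic visit.
2. Record the date of each skin visit.
3. Add a sensitivity analysis of the change scores with change in sun exposure as a covariate.
4. Add season to the limitations in 2.3.
5. State that month-3 changes in the sun-dependent features describe change over the season and are not, on their own, evidence of product effectiveness, whatever the adjusted result shows.

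**Cost:** three repeated questions, one date field and a few sentences. Self-report is coarse and the exposure change runs closely with time on product, so the adjustment is only partial and the conclusion becomes more cautious.
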